# 3.1.2 Dose regimen

Four single doses of 50 mg of riluzole (2 as test and 2 as reference formulation) will be administered to each volunteer in 4 subsequent study periods, separated by wash-out intervals of at least 7 days.

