#### **8.2** Treatment allocation

The study subjects will be assigned to one of 2 sequences of treatments (either RTRT or TRTR) according to their randomisation number. Randomisation number will be given to the subjects on study Day -1, period 1, as soon as they are definitely enrolled in the study.

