## 9.1.2 Secondary variables

- $ightharpoonup AUC_{0-\infty}$ ,  $t_{1/2}$ ,  $t_{max}$ ,  $AUC_{extra}$ ,  $\lambda_{z_{s}}$  of riluzole after replicate single dose administration of test and reference;
- Palatability score
- > TEAEs, vital signs (BP, HR), laboratory parameters, physical examination including BW

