# 10 STATISTICAL METHODS

The data documented in this study and the parameters measured will be evaluated and compared using classic descriptive statistics, i.e. geometric mean (PK data only), arithmetic mean, SD, CV (%), minimum, median and maximum values for quantitative variables, and frequencies for qualitative variables.

Not available data will be evaluated as "missing values". The statistical analysis of demographic and safety data will be performed using SAS® version 9.3 (TS1M1) (13) or higher (the actual versions will be stated in the final report).

The statistical analysis of PK parameters will be performed using Phoenix WinNonlin® version 6.3 (12) or higher and SAS® version 9.3 (TS1M1) or higher.

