Table 10.6.2.1 Examples of widened bioequivalence acceptance limits of  $C_{max}$  according to its actual  $CV_{WR}$ 

CV WR %*	Lower Limit	Upper Limit
30	80.00	125.00
35	77.23	129.48
40	74.62	134.02
45	72.15	138.59
≥50	69.84	143.19

\*:  $CVWR(\%) = 100\sqrt{e^{S^2WR} - 1}$ ; source: reference (9)

tmax and t1/2will be compared between treatments by the non-parametric Friedman test.

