8.6.2 Descriptive pharmacokinetics/pharmacodynamics

A descriptive PK will be presented.

Individual subject concentrations of riluzole will be presented in data listings (Listing 16.2.5.4) and summarised at each time point by treatment (Table 14.2.1.1).

Individual (figures in section 16.2.5) and mean curves (+SD at sampling times) (figures in section 14.2.1), indicating inter-subject variability, will be plotted. Mean curves will be presented by treatment.

PK parameters of riluzole will be listed (Listing 16.2.6.1) and summarised by treatment (Table 14.2.2.1).

Data below the lower quantification limit (BLQL) will be considered as 0 in the calculations and presented as BLQL in listings and tables. As a consequence of BLQL (i.e. 0) values, calculated geometric means (if requested) could be null. For this reason, in the presence of any null value, the geometric mean will be reported as NC. If for an individual PK curve, a log-linear regression with a correlation coefficient $R^2 > 0.8$ cannot be obtained, the extrapolated PK parameters will be reported as NC and considered missing in the calculations of descriptive statistics.

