Max	XXX.X	XXX.X	XXX.X	XXX.X	XXX.X	XXX.X	XXX.X	XXX.X	XXX.X	XXX.X	XXX.X	XXX.X	XXX.X	XXX.X	XXX.X

BLQL: Below Lower Quantification Limit (x.xx ng/mL)

Source: Listing 16.2.5.4 - Riluzole concentrations (ng/mL) measured in plasma

Program: pk-analysis\k344-tlf.sas

Statistical analysis plan CRO-PK-20-344 Sponsor code Z7251J01 Riluzole orodispersible film replicate bioavailability Final version 1.0, 31MAY21

Table 14.2.1.1 - Riluzole concentrations (ng/mL) measured in plasma - PK Set

Statistics	Pre dose	0.25 h	0.5 h	0.75 h	1 h	1.25 h	1.5 h	2 h	3 h	4 h	6 h	8 h	12 h	18 h	24 h
Ν	XX	XX	XX	XX	XX	XX	XX	XX	XX	XX	XX	XX	XX	XX	XX
Geo.Mean	XXX.XX	XXX.XX	XXX.XX	XXX.XX	XXX.XX	XXX.XX	XXX.XX	XXX.XX	XXX.XX	XXX.XX	XXX.XX	XXX.XX	XXX.XX	XXX.XX	XXX.XX
Mean	XXX.XX	XXX.XX	XXX.XX	XXX.XX	XXX.XX	XXX.XX	XXX.XX	XXX.XX	XXX.XX	XXX.XX	XXX.XX	XXX.XX	XXX.XX	XXX.XX	XXX.XX
SD	XXX.XX	XXX.XX	XXX.XX	XXX.XX	XXX.XX	XXX.XX	XXX.XX	XXX.XX	XXX.XX	XXX.XX	XXX.XX	XXX.XX	XXX.XX	XXX.XX	XXX.XX
CV%	XXX.XX	XXX.XX	XXX.XX	XXX.XX	XXX.XX	XXX.XX	XXX.XX	XXX.XX	XXX.XX	XXX.XX	XXX.XX	XXX.XX	XXX.XX	XXX.XX	XXX.XX
Min	XXX.X	XXX.X	XXX.X	XXX.X	XXX.X	XXX.X	XXX.X	XXX.X	XXX.X	XXX.X	XXX.X	XXX.X	XXX.X	XXX.X	XXX.X
Median	XXX.XX	XXX.XX	XXX.XX	XXX.XX	XXX.XX	XXX.XX	XXX.XX	XXX.XX	XXX.XX	XXX.XX	XXX.XX	XXX.XX	XXX.XX	XXX.XX	XXX.XX
Max	XXX.X	XXX.X	XXX.X	XXX.X	XXX.X	XXX.X	XXX.X	XXX.X	XXX.X	XXX.X	XXX.X	XXX.X	XXX.X	XXX.X	XXX.X

BLQL: Below Lower Quantification Limit (x.xx ng/mL)

Source: Listing 16.2.5.4 - Riluzole concentrations (ng/mL) measured in plasma

Program: pk-analysis\k344-tlf.sas

Statistical analysis plan CRO-PK-20-344 Sponsor code Z7251J01 Riluzole orodispersible film replicate bioavailability Final version 1.0, 31MAY21

Table 14.2.2.1 - Riluzole plasma PK parameters - PK Set

Investigational Medicinal Product: Riluzole 50 mg orodispersible film (T)

Statistics	C _{max} (ng/mL)	t _{max} (h)	AUC _{0-t} (h*ng/mL)	AUC _{0-inf} (h*ng/mL)	t½ (h)	λz (1/h)
N	XX	XX	XX	XX	XX	XX
Geo.Mean	XXX.XX	XXX.XX	XXX.XX	XXX.XX	XXX.XX	XXX.XX
Mean	XXX.XX	XXX.XX	XXX.XX	XXX.XX	XXX.XX	XXX.XX
SD	XXX.XX	XXX.XX	XXX.XX	XXX.XX	XXX.XX	XXX.XX
CV%	XXX.XX	XXX.XX	XXX.XX	XXX.XX	XXX.XX	XXX.XX
Min	XXX.XX	XXX.XX	XXX.XX	XXX.XX	XXX.XX	XXX.XX
Median	XXX.XX	XXX.XX	XXX.XX	XXX.XX	XXX.XX	XXX.XX
Max	XXX.XX	XXX.XX	XXX.XX	XXX.XX	XXX.XX	XXX.XX

Source: Listing 16.2.6.1 - Riluzole plasma PK parameters Program: pk-analysis\k344-tlf.sas

Statistical analysis plan CRO-PK-20-344 Sponsor code Z7251J01 Riluzole orodispersible film replicate bioavailability Final version 1.0, 31MAY21

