Table 14.2.2.1 - Riluzole plasma PK parameters - PK Set

Investigational Medicinal Product: Rilutek®, 50 mg riluzole tablets (R)

Statistics	C _{max} (ng/mL)	t _{max} (h)	AUC _{0-t} (h*ng/mL)	AUC _{0-inf} (h*ng/mL)	t½ (h)	λz (1/h)
N	XX	XX	XX	XX	XX	XX
Geo.Mean	XXX.XX	XXX.XX	XXX.XX	XXX.XX	XXX.XX	XXX.XX
Mean	XXX.XX	XXX.XX	XXX.XX	XXX.XX	XXX.XX	XXX.XX
SD	XXX.XX	XXX.XX	XXX.XX	XXX.XX	XXX.XX	XXX.XX
CV%	XXX.XX	XXX.XX	XXX.XX	XXX.XX	XXX.XX	XXX.XX
Min	XXX.XX	XXX.XX	XXX.XX	XXX.XX	XXX.XX	XXX.XX
Median	XXX.XX	XXX.XX	XXX.XX	XXX.XX	XXX.XX	XXX.XX
Max	XXX.XX	XXX.XX	XXX.XX	XXX.XX	XXX.XX	XXX.XX

Source: Listing 16.2.6.1 - Riluzole plasma PK parameters Program: pk-analysis\k344-tlf.sas

Statistical analysis plan CRO-PK-20-344 Sponsor code Z7251J01 Riluzole orodispersible film replicate bioavailability Final version 1.0, 31MAY21

Analysis	Dependent Variable	Comparison	Point Estimate	90% Confidence Interval Lower Limit	90% Confidence Interval Upper Limit	Effect	p Value
ANOVA	Ln(AUC _{0-inf})	T vs R	XXX.XX	XXX.XX	XXX.XX		
						Sequence	X.XXXX
						Treatment	X.XXXX
						Period	X.XXXX
ANOVA	Ln(AUC _{0-t})	T vs R	XXX.XX	XXX.XX	xxx.xx		
						Sequence	XXXXX
						Treatment	X.XXXX
						Period	X.XXXX
ANOVA	Ln(C _{max})	T vs R	XXX.XX	XXX.XX	XXX.XX		
						Sequence	X.XXXX
						Treatment	X.XXXX
						Period	X.XXXX

Table 14.2.3.1 - Statistical analysis on riluzole plasma PK parameters - PK set

T: Riluzole 50 mg orodispersible film (T)

R: Rilutek[®], 50 mg riluzole tablets (R) _

Program: pk-analysis\k344-tlf.sas

Statistical analysis plan CRO-PK-20-344 Sponsor code Z7251J01 Riluzole orodispersible film replicate bioavailability Final version 1.0, 31MAY21

Table 14.2.3.2 - Within-subject variability of C_{max} (after administration of the reference formulation) - PK Set

AINGR	Dependent Variable	${S^2}_{WR}$	Within-subject variability CV _{WR} (%)
Riluzole	Ln(C _{max})	XXX.XXX	XX.XX

Note: CV_{WR} % was calculated by applying the formula 100*sqrt[exp(S^2_{WR})-1] Program: pk-analysis\k344-tlf.sas

Statistical analysis plan CRO-PK-20-344 Sponsor code Z7251J01 Riluzole orodispersible film replicate bioavailability Final version 1.0, 31MAY21

Table 14.2.3.3 - Non-parametric Friedman test on t_{max} and $t_{1/2}$ - PK set

Analysis	Dependent Variable	Comparison	p Value
Friedman	t _{max}	T vs R	X.XXXX
	t _{1/2}	T vs R	X.XXXX

Program: pk-analysis\k344-tlf.sas

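### Does the plan need to say how replicate tmax and t1/2 values enter the Friedman test, and which error term the Sequence p-value uses?

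*Protocol*

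**What the plan says.** Protocol 3.1.2 gives each volunteer "Four single doses of 50 mg of riluzole (2 as test and 2 as reference formulation"), and Protocol 8.2 adds: "The study subjects will be assigned to one of 2 sequences of treatments (either RTRT or TRTR"). A completer therefore has two tmax and two t1/2 values for each product. Protocol 9.1.2 lists both among the secondary variables "of riluzole after replicate single dose administration of test and reference".

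For their comparison, Protocol 10.6.2 says only that they "will be compared between treatments by the non-parametric Friedman test". SAP 8.6.3 repeats this and points to the shell headed "Table 14.2.3.3 - Non-parametric Friedman test on" tmax and t1/2, which has one p-value per variable on a line labelled T vs R. The medians and ranges appear by product in "Table 14.2.2.1 - Riluzole plasma PK parameters - PK Set". No shell has a test-minus-reference difference or interval for tmax or t1/2.

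Where the log-linear fit is inadequate, SAP 8.6.2 says "the extrapolated PK parameters will be reported as NC and considered missing in the calculations of descriptive statistics". Protocol 10 has a general rule ("Not available data will be evaluated as" missing).

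For log Cmax and log AUC, Protocol 10.6.2 and SAP 8.6.3 list treatment, period, sequence and subject within sequence as fixed effects. The same sections also call the model mixed. SAP Table 14.2.3.1 prints p-values for Sequence, Treatment and Period, and SAP 8.1 puts an asterisk on any p-value below 0.05. Both sections also describe the two one-sided tests as having bioequivalence as the null hypothesis.

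**The concern.** The ordinary Friedman test takes one value per subject per treatment, and this design yields two. Someone has to choose a layout, and in an open-label study a layout chosen late could be chosen with the data in view. Different layouts can fall on different sides of 0.05. A subject with one non-calculable t1/2 might be dropped or kept, which changes the sample.

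Sequence varies only between subjects. If every effect is fixed and no error term is named, the literal default is the residual, which contains only within-subject variation. The Sequence test is then far too liberal, and a spurious asterisk could appear in the table that carries the primary results.

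At stake are a p-value for each of two secondary variables and a diagnostic p-value that might need explaining in the study report.

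**Working it through.** There is no figure in the plan to reproduce here. The check is how much each open choice could move the output.

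**1. Friedman layout.** Trials were simulated with 26 RTRT and 26 TRTR subjects and lognormal tmax (assumed median 0.75 h, no subject-by-product interaction), with values moved to the nearest planned sampling time and 4,000 trials per setting. The between- and within-subject log-SDs are assumptions; the documents give none for tmax. Power at the 5% level:

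| Log-SDs (between/within) | T/R ratio | Averaged per product | Four values ranked within subject | Signed-rank on means | Four separate columns |
|---|---|---|---|---|---|
| 0.25/0.35 | 1.15 | 63% | 72% | 74% | 55% |
| 0.25/0.35 | 1.20 | 86% | 92% | 92% | 81% |
| 0.30/0.50 | 1.20 | 55% | 65% | 65% | 47% |
| 0.30/0.50 | 1.25 | 72% | 82% | 82% | 66% |

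With no true difference and no period effect, all four reject in 4.5 to 5.2% of trials.

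The four-column layout compares four conditions on 3 degrees of freedom. It does not answer T vs R, which is what the shell announces. Under assumed period drifts its size rises to 8% or 25%, but nothing in the documents suggests such drifts in tmax, and the other three layouts stay at 5.0 to 5.4%. The averaged and within-subject-ranked layouts both fit the shell, and their powers differ by 72 − 63 = 9, 92 − 86 = 6, 65 − 55 = 10 and 82 − 72 = 10 points. Replacing Friedman by the signed-rank test gains at most 74 − 72 = 2 points over the ranked layout.

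**2. Non-calculable t1/2.** If a proportion p of profiles is non-calculable at random, the expected number of the 52 subjects with all four values is 52(1 − p)^4, and with at least one value per product 52(1 − p²)². The rates are assumed.

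| p | All four values | At least one per product |
|---|---|---|
| 5% | 42.4 | 51.7 |
| 10% | 34.1 | 51.0 |
| 20% | 21.3 | 47.9 |

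Setting the single non-calculable value to missing follows the plan's own rule and keeps nearly everyone. Nothing in the documents points to a rate as high as 20%.

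**3. Sequence p-value.** With 52 × 4 = 208 observations, residual degrees of freedom are 207 − 51 − 3 − 1 = 152. Log-scale variances come from s² = ln(1 + CV²), and the between-subject part is total minus within. With no true sequence effect, the Sequence mean square exceeds the residual in expectation by r = (sW² + 4sB²)/sW². The false-positive rate is P(F(1,152) > 3.903/r). Inputs are from Protocol Table 1.4.1.1: the within-subject CVs, and the total CVs for film without water (13 subjects) and tablet (12 subjects).

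| Variable | Within CV | Total CV (film; tablet) | r | False-positive rate |
|---|---|---|---|---|
| Cmax | 32.13% | 38.44%; 48.32% | 2.61; 5.54 | 22.3%; 40.3% |
| AUC0-t | 18.43% | 25.10%; 38.95% | 4.32; 13.9 | 34.3%; 59.7% |
| AUC0-∞ | 18.62% | 25.97%; 39.90% | 4.66; 14.3 | 36.2%; 60.3% |

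For Cmax on the tablet: sW² = 0.0983, total 0.2098, sB² = 0.1116, so r = 1 + 4 × 0.1116/0.0983 = 5.54.

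The film-with-water CVs in Table 1.4.1.2 are left out. That table reports arithmetic means below the geometric means (Cmax 180.950 against 206.394), which cannot come from one set of values, and film with water is not how the film is given here.

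Tested against subject within sequence, on 1 and 50 degrees of freedom, the rate is 5%; simulation gave 4.9 to 5.4%. The test/reference estimate and its 90% interval do not use the Sequence error term.

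**The case for a change.** The strongest opposing case is that a SAP exists to close such choices before database lock. Four readings of the Friedman test (averaged, ranked within subject, four conditions, and 104 separate pairs) disagreed about p < 0.05 in 10% of simulated trials with no difference and in 31% with a log shift of 0.1. Closing the gap would cost a few sentences. The liberal Sequence test follows from taking the fixed-effects list at its word and using the protocol's own pilot CVs.

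The silence in the text is real, and so is the arithmetic. Its consequence is not established. The disagreement figures include the four-condition layout, which the T vs R label excludes. Two valid tests on the same data will sometimes differ around 0.05, and that does not make either one wrong. On Sequence, the fixed-effects list points to the residual, but the mixed-model sentence beside it points to a between-subject test, so the faulty test is one of two readings. Removing that sentence would not be an editorial matter: it would choose the model for the primary variables, and fixed and random subject effects can give different estimates when periods are missing.

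**Conclusion.** No change follows. The plan leaves three details open: the Friedman layout for replicates, the handling of a subject with a non-calculable t1/2, and the Sequence error term. Each has a sensible reading that is compatible with the text: average or rank within subject, keep the values that are available, and test Sequence between subjects. Bioequivalence rests on the 90% intervals for Cmax and AUC0-t, which none of these choices enters. The choice between the two natural Friedman layouts moves power by 6 to 10 points and leaves size at about 5%; switching to a signed-rank test gains next to nothing over the ranked layout. A Sequence asterisk would be a diagnostic without a decision attached, and a statistician can check its error term when reading the table. Naming bioequivalence as the null hypothesis is a clerical reversal, since the sample-size text in Protocol 10.2 and SAP 8.3 states the nulls as non-equivalence.

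The tmax figures rest on assumed log-SDs, a lognormal shape and no subject-by-product interaction; the t1/2 counts rest on assumed rates of non-calculable profiles. The Sequence rates rest on CVs from 12 or 13 pilot subjects and should be read as rough sizes.

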#### 10.7 Safety and tolerability evaluation

#### > AEs

AEs will be coded by System Organ Class (SOC) and Preferred Term (PT), using the Medical Dictionary for Regulatory Activities (MedDRA).

AEs will be classified as pre-treatment AEs (PTAEs) and TEAEs, according to the period of occurrence, as follows:

- > PTAEs: all AEs occurring before the first dose of IMP and not worsening after the first dose of IMP
- > TEAEs: all AEs occurring or worsening after the first dose of IMP

Individual PTAEs and TEAEs will be listed in subject data listings. No summary table will be provided for PTAEs. TEAEs will be summarised by treatment and overall. The number and percentage of subjects with any TEAE and the number of TEAEs will be tabulated by SOC and PT, seriousness, relationship to treatment and severity.

#### Physical examination

Date of the physical examination, overall investigator's interpretation (as normal or abnormal and, if abnormal, clinically significant or not clinically significant) and clinically significant abnormalities (if any) will be listed.

#### > Laboratory data

Date/time of samples collection, overall investigator's interpretation (as normal or abnormal and, if abnormal, clinically significant or not clinically significant) and clinically significant findings (if any) will be listed. All laboratory results will be listed and a table of all the abnormal values will be presented. The overall investigator's interpretation will be summarised using tables of frequency.

#### > Vital signs

Vital signs values will be listed and summarised by descriptive statistics.

#### **Body weight**

Body weight values will be listed and summarised by descriptive statistics.

## > Tolerability at the application site

Date/time of each mouth visual inspection, overall investigator's interpretation (as normal or abnormal and, if abnormal, clinically significant or not clinically significant) and clinically significant findings (if any) will be listed.

## 11 DEFINITION AND HANDLING OF AES AND SAES

## 11.1 Applicable SOPs

AEs definition, classification and management will follow the Sponsor's SOPs. The AE form present in the CRF and the SAE form will also follow the sponsor SOPs.

The full SOP or an operative summary will be made available to the Phase I Unit.

A brief summary of AE definition, classification and management is reported below.

## 11.2 Definition of Adverse Event (AE)

An AE is "any untoward medical occurrence in a patient or clinical study subject administered a medicinal product and which does not necessarily have a causal relationship with treatment".

#### AEs include:

- worsening (change in nature, severity or frequency) of conditions present at the onset of the study
- > patient/subject deterioration due to the primary illness
- > intercurrent illnesses
- drug interactions
- > events related or possibly related to concomitant medications
- ➤ abnormal laboratory values, as well as significant shifts from baseline within the range of normal, which the investigator considers to be clinically significant.

An AE can therefore be any unfavourable and unintended sign (including an abnormal laboratory finding), symptom, or disease temporally associated with the use of an investigational medicinal product, whether or not considered related to the investigational medicinal product.

#### 11.3 Definition of Adverse Drug Reaction (ADR)

An ADR is "any untoward and unintended response to a medicinal product related to any dose administered".

All AEs judged by either the reporting investigator or the sponsor as having a reasonable causal relationship to a medicinal product qualify as adverse reactions. The expression reasonable causal relationship means to convey in general that there is evidence or matter to suggest a causal relationship.

#### ➤ Unexpected ADR:

an unexpected ADR is: "An adverse reaction, the nature or severity of which is not consistent with the applicable product information (Reference Safety Information - RSI)"

➤ Reference Safety Information (RSI): in order to assess whether an ADR is expected, the IB will be used.

#### 11.4 Definition of Serious Adverse Events or Serious Adverse Drug Reaction

A Serious Adverse Event (SAE) or Serious Adverse Drug Reaction (SADR) is: "any untoward medical occurrence or effect that at any dose":

- results in death
- ➤ is life-threatening (i.e. the subject was at risk of death at the time of the event/reaction; it does not refer to an event/reaction which hypothetically might have caused death if it were more severe)
- requires inpatient hospitalisation or prolongation of existing hospitalisation
- results in persistent or significant disability/incapacity (where disability is defined as a permanent or substantial disruption of ability to carry out normal life functions, either reported or defined as per clinical judgement)
- is a congenital anomaly/birth defect
- is an important medical event that may not result in death, be life-threatening, or require hospitalization but, according to appropriate medical judgment, it may jeopardize the subject's health status and may require intervention to prevent any of the outcomes listed in the definition above. Examples of such events include allergic bronchospasm requiring intensive treatment in an emergency room or at home or blood dyscrasias or convulsions that do not result in hospitalisation or development of drug dependency or drug abuse

Any suspected transmission via a medicinal product of an infectious agent is also considered a serious adverse event.

A Suspected Unexpected Serious Adverse Reaction (SUSAR) is an ADR that is both unexpected (not consistent with the RSI) and also meets the definition of a SAE.

A non-serious adverse event is any adverse event that does not meet the criteria listed above for a serious adverse event.

## 11.5 Definition of Severity of Adverse Events

The term "severe" is used to describe the intensity (severity) of a specific event:

- Mild: causing no limitation of usual activities; the subject may experience slight discomfort.
- Moderate: causing some limitation of usual activities; the subject may experience annoying discomfort.
- Severe: causing inability to carry out usual activities; the subject may experience intolerable discomfort or pain.

## 11.6 Definition of Adverse Event causality

Causality shall be determined according to the definition of ADR given in 11.3.

All AE judged by either the investigator or the sponsor as having a reasonable suspected causal relationship to an investigational medicinal product qualify as adverse reactions. The causality assessment given by the investigator should not be downgraded by the sponsor.

The following binary decision for causality will be used:

- Reasonable possibility that the IMP caused the event
- No reasonable possibility that the IMP caused the event

Features supportive of an association include:

- temporal plausibility
- pharmacological properties of the drug or of the substance class
- course of the adverse event after dechallenge and, if applicable, after rechallenge
- specific tests indicating involvement of the drug in the occurrence/worsening of the adverse event
- alternative explanations

### 11.7 Adverse Events recording

Each AE occurring to a subject, either spontaneously revealed by the subject or observed by the investigator, whether believed by the investigator to be related or unrelated to the IMP, must be recorded on the AE information page of the CRF (for SAEs information must be recorded also on the "Serious Adverse Event Form").

The investigator will also perform an evaluation with respect to seriousness and causality (relationship of any AE to IMP) of the AEs and record it on the appropriate section of the CRF and on the "Serious Adverse Event Form" (if appropriate).

